3.1.1 Administrative structure of the trial

The trial is sponsored by Boehringer Ingelheim (BI) Pharma GmbH & Co. KG, Germany.

BI has appointed a Trial Clinical Monitor, responsible for coordinating all required activities, in order to

- Manage the trial in accordance with applicable regulations and internal SOPs,
- Direct the clinical trial team in the preparation, conduct, and reporting of the trial,
- Ensure appropriate training and information of local clinical monitors (CML), Clinical Research Associates (CRAs), and participating trial sites.

The radiolabelled trial medication (BI 425809 XX (C-14)) will be provided by

The trial will be conducted at
under the supervision of the Principal Investigator.

Safety laboratory tests will be performed by the local laboratory of the trial site

The analyses of BI 425809 (and its metabolites) concentrations in plasma, the metabolite profiling and the identification in urine, plasma, and faeces will be performed at BI and/or at a suitable Contract Research Organisation (CRO) under the responsibility of the Department of Drug Metabolism and Pharmacokinetics, BI Pharma GmbH & Co. KG, Biberach, Germany .

Blood, plasma, urine, and faeces (and vomit if applicable) concentrations of [¹⁴C]-radioactivity will be determined at

On-site monitoring will be performed by BI or a contract research organisation appointed by BI.

Data management and statistical evaluation will be performed by BI according to BI SOPs and/or by a suitable CRO under the responsibility of the Department of Biostatistics and Data Sciences, BI Pharma GmbH & Co. KG, Biberach, Germany.

Tasks and functions assigned in order to organize, manage, and evaluate the trial are defined according to BI SOPs. A list of responsible persons and relevant local information can be found in the ISF.

3.2 DISCUSSION OF TRIAL DESIGN, INCLUDING THE CHOICE OF CONTROL GROUP

This is a standard study design for a [^{14}C] human study of absorption, metabolism, and excretion including determination of mass balance.

Inclusion of a control group is not required for this investigation. Due to the prolonged half-life of the metabolite BI 761036 (M232) (~170h), that contains the radioactive [^{14}C] label, it cannot be excluded that prolonged sampling is necessary in humans. Therefore, following 14 days in-house excreta collection after dosing, subjects will return on a weekly basis for in-house 24-h collection intervals for up to 7 weeks after dosing as long as release criteria are not met ([Section 3.1](#)).

Blinding is not necessary, because all subjects receive the same treatment.

3.3 SELECTION OF TRIAL POPULATION

It is planned that 6 healthy male subjects will enter the study. They will be recruited from the volunteers' pool of the trial site or, if necessary, via advertisement. In case a subject vomits within 8 h after trial drug administration assuming an incomplete absorption of the radiolabelled compound an additional subject may be entered and dosed to assure that 6 evaluable subjects will complete the study as per protocol. Thereby, the actual number of subjects entered may increase up to 8.

The current trial is designed to investigate the basic pharmacokinetics of BI 425809 including absorption, metabolism, and elimination and quantitative determination of excretion by mass balance. Samples will be generated for additional metabolic profiling and structural identification. Healthy male subjects are an ideal population for the objectives of this trial, since they provide relatively stable physiological, biochemical and hormonal conditions, i.e. the absence of disease-related variations and relevant concomitant medications.

A log of all subjects enrolled into the trial (i.e. having given informed consent) will be maintained in the ISF at the investigational site irrespective of whether they have been treated with investigational drug or not.

3.3.1 Main diagnosis for study entry

The study will be performed in healthy subjects.

3.3.2 Inclusion criteria

Subjects will only be included into the trial, if they meet the following criteria:

1. Healthy male subjects according to the investigator's assessment, based on a complete medical history including a physical examination, vital signs (BP, PR), 12-lead ECG, and clinical laboratory tests
2. Age of 18 to 65 years (incl.)
3. BMI of 18.5 to 29.9 kg/m² (incl.)

4. Signed and dated written informed consent prior to admission to the study in accordance with GCP and local legislation
5. Subjects who are sexually active must use, with their partner, highly effective contraception from the time of administration of trial medication until 4 months after administration of trial medication. Adequate methods are:
 - Condoms plus use of hormonal contraception by the female partner that started at least 2 months prior to administration of trial medication (e.g., implants, injectables, combined oral or vaginal contraceptives, intrauterine device) or
 - Condoms plus surgical sterilization (vasectomy at least 1 year prior to enrolment) or
 - Condoms plus surgically sterilised partner (including hysterectomy) or
 - Condoms plus intrauterine device or
 - Condoms plus partner of non-childbearing potential (including homosexual men)

Subjects are required to use condoms to prevent unintended exposure of the partner to the study drug via seminal fluid.

Alternatively, true abstinence is acceptable when it is in line with the subject's preferred and usual lifestyle. If a subject is usually not sexually active but becomes active, with their partner, they must comply with the contraceptive requirements detailed above.

3.3.3 Exclusion criteria

Subjects will not be allowed to participate if any of the following general criteria apply:

1. Any finding in the medical examination (including BP, PR or ECG) is deviating from normal and judged as clinically relevant by the investigator
2. Repeated measurement of systolic blood pressure outside the range of 90 to 139 mmHg, diastolic blood pressure outside the range of 45 to 89 mmHg, or pulse rate outside the range of 40 to 100 bpm
3. Any laboratory value outside the reference range that the investigator considers to be of clinical relevance
4. Any evidence of a concomitant disease judged as clinically relevant by the investigator
5. Clinically significant gastrointestinal, hepatic, renal, respiratory (including but not limited to interstitial lung disease), cardiovascular, metabolic, immunological or hormonal disorders
6. Cholecystectomy and/or surgery of the gastrointestinal tract that could interfere with the pharmacokinetics of the trial medication (except appendectomy and simple hernia repair)
7. Diseases of the central nervous system (including but not limited to any kind of seizures or stroke), and other relevant neurological or psychiatric disorders
8. History of relevant orthostatic hypotension, fainting spells, or blackouts
9. Chronic or relevant acute infections

10. History of relevant allergy or hypersensitivity (including allergy to the trial medication or its excipients)
11. Use of drugs within 30 days prior to administration of trial medication if that might reasonably influence the results of the trial (incl. QT/QTc interval prolongation). Use of CYP3A4 inhibitors and inducers 1 week prior to administration of trial medication
12. Participation in another trial where an investigational drug has been administered within 60 days prior to planned administration of trial medication, or current participation in another trial involving administration of investigational drug
13. Smoker (more than 5 cigarettes or 1 cigars or 1 pipes per day)
14. Inability to refrain from smoking on trial days
15. Average intake of more than 24 units of alcohol per week (1 unit of alcohol equals approximately 250 mL of beer, 100 mL of wine or 35 ml of spirits)
16. Drug abuse or positive drug screening
17. Blood donation of more than 100 mL within 30 days prior to administration of trial medication or intended donation during the trial
18. Intention to perform excessive physical activities within 4 days prior to administration of trial medication or during the trial
19. Inability to comply with dietary regimen of trial site
20. A marked baseline prolongation of QT/QTc interval (such as QTc intervals that are repeatedly greater than 450 ms) or any other relevant ECG finding at screening
21. A history of additional risk factors for Torsades de Pointes (such as heart failure, hypokalemia, or family history of Long QT Syndrome)
22. Subject is assessed as unsuitable for inclusion by the investigator, for instance, because considered not able to understand and comply with study requirements, or has a condition that would not allow safe participation in the study

In addition, the following trial-specific exclusion criteria apply:

23. Participation in another ADME study with a radiation burden of >0.1 mSv in the period of 1 year prior to screening or 1.1-2.0 mSv in the past 2 years or 2.1-3.0 mSv in the past 3 years etc.
24. Exposure to radiation for diagnostic reasons (except dental X-rays and plain X-rays of thorax and bony skeleton (excluding spinal column)) in the period of 1 year prior to screening
25. Irregular defecation pattern (less than a mean of one bowel movement every day)

For study restrictions, refer to [Section 4.2.2](#).

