The major human metabolites of BI 425809, M530 (BI 758790) and M232 (BI 761036), have been evaluated in nonclinical studies with no evidence of pharmacological activity, genotoxicity, effects on embryo-foetal development, or adverse effects in repeat-dose toxicity in studies of 13 – 15 weeks duration.

Furthermore, multiple doses of up to 75 mg twice daily (150 mg/d) were well tolerated in previous clinical trials. Based on this human data there is no indication of a metabolite-mediated safety concern for a single dose administration of 25 mg BI 425809 in the present trial.

Risks related to administration of BI 425809XX (C-14)

BI 425809 XX (C-14) is labelled with the isotope [¹⁴C] which is necessary for the purposes of this mass balance trial. Therefore, subjects will be exposed to ionizing radiation. The effective dose that each subject receives from one administration of 3.7 MBq is approx. 0.41 mSv.

The radioactive dose proposed for administration in the planned human ADME study, 0.41 mSv, is lower than the limit specified by:

WHO Category 1, (<0.5mSv – within variations of natural background radioactivity)

And lower than the limit proposed by:

ICRP Category 2a, (<1 mSv – risk defined as minor)

For details on the radiation burden calculation please refer to [Appendix 10.1](#).

For clinical investigations to study the disposition, metabolism and excretion of new pharmaceutical compounds in man an effective dose of 0.1 – 1.0 mSv is considered acceptable [[R15-3219](#)].

Summary of benefit-risk assessment

In previous trials in healthy subjects, administration of single oral doses up to 150 mg BI 425809 and multiple oral doses up to 75 mg BI 425809 once or twice daily was safe and well tolerated ([Section 1.2.4](#)). In the current trial, healthy male volunteers will receive a single oral dose of 25 mg BI 425809. Each participating subject will receive only one radioactive dose.

The trial design is optimized to collect as much relevant information as possible on the pharmacokinetics of BI 425809 without exposing participating volunteers to undue risk. However, there is always the potential for subjects receiving medication to experience

adverse events (AEs), and rarely also serious adverse events (SAEs). Risks to subjects will be minimized and addressed by eligibility criteria, safety laboratory examinations, ECG and vital sign measurements, in-house observation periods and verbal communication concerning AEs.

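### Exclusion criterion 23 limits earlier research radiation only if it came from an ADME study; the same exposure from other research meets no specific exclusion

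*Protocol*

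**What the plan says.** Four exclusion criteria in Protocol Section 3.3.3 bear on a volunteer's earlier research or radiation history.

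- **Criterion 23** is the only one with a numerical radiation limit. It excludes for "Participation in another ADME study with a radiation burden of >0.1 mSv in the period of 1 year prior to screening", and then for "1.1-2.0 mSv in the past 2 years or 2.1-3.0 mSv in the past 3 years etc". The longer bands depend on the same opening phrase, so they too apply to ADME studies.
- **Criterion 24** excludes for "Exposure to radiation for diagnostic reasons" in the year before screening, apart from dental X-rays and certain plain films. It sets no dose limit and does not name research exposure.
- **Criterion 12** excludes for "Participation in another trial where an investigational drug has been administered within 60 days prior to planned administration of trial medication", or for being in such a trial at present. It does not refer to radiation.
- **Criterion 22** is general: "Subject is assessed as unsuitable for inclusion by the investigator". The examples it gives concern understanding, compliance and conditions that make participation unsafe. Radiation history is not among them.

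None of the inclusion criteria in Section 3.3.2 mentions radiation. On recruitment, Section 3.3 says: "They will be recruited from the volunteers' pool of the trial site", with advertisement as a fallback.

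**The concern.** Criterion 23 exists because the sponsor regards recent research radiation as a reason not to dose a healthy man again. The reason lies in the radiation received, yet the criterion is triggered by the type of study that delivered it. A research scan with a tracer, or a radiolabelled study with some purpose other than ADME, can expose a volunteer just as an ADME study can, and criterion 23 does not count it.

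What is at stake is subject protection. Section 2.3 states that participants receive no therapeutic benefit. Criteria 12 and 23 show that the sponsor expects some candidates to have been in earlier trials. If a numerical limit is thought necessary for one kind of research exposure, one would expect it to cover the others or the protocol to give a reason for leaving them out. It gives none.

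**Working it through.** No statistical formula applies. The check is to read every eligibility criterion for a rule that would catch non-ADME research radiation, and then to apply the criteria to matched cases.

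**Inputs from the Protocol**

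- One-year trigger: above 0.1 mSv, ADME study only, counted back from screening (criterion 23).
- Diagnostic radiation: one year, counted back from screening (criterion 24).
- Other trials: 60 days, investigational drug given, counted back from planned dosing (criterion 12).
- Investigator discretion: no limit and no time window (criterion 22).
- For scale, this trial's own burden: "The effective dose that each subject receives from one administration of 3.7 MBq is approx. 0.41 mSv" (Section 2.3). With the factor in Section 3.1, 3.7 MBq × 0.111 mSv/MBq = 0.4107 mSv, which reproduces the stated 0.41 mSv.

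**Matched cases.** The 0.2 mSv dose and the dates are assumptions chosen for illustration; any dose above 0.1 mSv gives the same result.

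| Case | Earlier exposure | Crit. 23 | Crit. 24 | Crit. 12 | Result |
|---|---|---|---|---|---|
| A | ADME study, 0.2 mSv, 6 months before screening | Met | Not met | Not met | Excluded |
| B | Non-ADME research study, not for diagnosis, 0.2 mSv, 6 months before screening | Not met | Not met | Not met | No specific exclusion; criterion 22 only |
| C | As B, but within 60 days of dosing and with an investigational drug | Not met | Not met | Met | Excluded, though not because of the radiation |
| D | As B, within 60 days of dosing, no investigational drug | Not met | Not met | Not met | No specific exclusion; criterion 22 only |

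A and B differ only in the type of study. The dose, the timing and the lack of a diagnostic purpose are the same.

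**Extent of the gap.** Where an investigational drug was given, the gap opens once the 60 days of criterion 12 have passed and runs to the end of the one-year look-back. Where none was given, it covers the whole year. The two clocks start at different points: the Flow Chart puts screening at Day -21 to Day -2, so the boundaries shift by up to three weeks, but the gap does not close. The two-year and three-year bands have the same restriction, so older non-ADME exposures are not counted either.

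**Screening.** The procedures listed in the first Flow Chart footnote and in Section 5.2.5.2 include relevant medical history and a review of the criteria. A review of criterion 23 prompts a question about ADME studies. Nothing listed prompts one about other research radiation.

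**The case against.** The strongest reply is that such a man need not get in. Criterion 22 lets the investigator exclude anyone judged unsuitable, and its examples are not exhaustive. A site might also read criterion 24 broadly enough to take in research imaging, and criterion 12 already removes recent participants in drug trials. This stands in part. A reader might infer that a volunteer like case B is eligible; the documents support only that no specific criterion excludes him. But discretion does not replace a numerical rule that the sponsor chose to write, and a broad reading of criterion 24 goes beyond its wording.

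It can also be said that the practical effect is unknown. Section 3.3 says where volunteers come from, not how often they have had research radiation, and only 6 to 8 men are needed. That stands, and it limits the weight of the point.

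Three further inferences are tempting, and the documents do not support them.

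- *That the gap undermines the benefit-risk assessment.* Section 2.3 judges this trial's own 0.41 mSv against the categories it cites. It makes no argument from accumulated dose, so nothing there is contradicted.
- *That the bands in criterion 23 have holes between 1.0 and 1.1 mSv and between 2.0 and 2.1 mSv.* At the one-decimal precision used, they are contiguous.
- *That the 0.1 mSv trigger can be turned into an activity using 0.111 mSv/MBq.* That factor rests on assumptions specific to BI 425809 in Appendix 10.1, including a 170-hour half-life and the split between faeces and urine. It cannot be carried over to another compound, and criterion 23 is already in mSv.

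**Conclusion.** The point holds as a gap in scope. The only numerical limit on earlier research radiation is tied to ADME studies, and neither criterion 12 nor criterion 24 fills what is left. A non-ADME research exposure above 0.1 mSv in the past year meets no specific exclusion and is left to criterion 22, while an identical exposure from an ADME study excludes.

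The conclusion rests on reading *ADME study* and the diagnostic wording of criterion 24 in their ordinary sense. It does not depend on any assumed size of exposure beyond its being above the sponsor's own trigger. The documents give no basis for saying how many volunteers would be affected or how large their exposures might be, so no further magnitude is claimed.

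Whether criterion 23 adds exposures across several studies is unclear from its wording. That calls for clarification and is not shown to be an error.

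This is a matter of subject protection that is worth correcting because correction is cheap. The sample size, the PK endpoints and the descriptive analysis are unaffected.

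**What to change.** In criterion 23, replace *another ADME study* with *any research study involving ionising radiation*, and leave the rest as it stands: the open-ended limit above 0.1 mSv in one year, the two-year and three-year bands, and the closing *etc.* The bands should not be redrawn in passing. For example, capping the one-year limit at 1.0 mSv and stopping the bands at 3.0 mSv would, read literally, leave an exposure above 3.0 mSv six months earlier in no band, although the present text excludes it when it came from an ADME study.

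Three additions complete the change:

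- State whether exposures are summed across studies within each look-back period.
- Reconcile the wording with criterion 24, so that it is clear which of the two covers imaging done for research.
- Add a question on earlier research radiation to the screening procedures.

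If the restriction to ADME studies is deliberate, the protocol should say why.

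The cost is one reworded criterion and one screening question. A few volunteers from the pool may become ineligible, which is a small burden when 6 to 8 subjects are needed.

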3.3.4 Removal of subjects from therapy or assessments

3.3.4.1 Removal of individual subjects

An individual subject is to be removed from the trial if:

1. The subject withdraws consent for trial treatment or trial participation, without the need to justify the decision
2. The subject needs to take concomitant drugs that interfere with the investigational product or other trial medication
3. The subject is no longer able to participate for other medical reasons (such as surgery, adverse events, or diseases)
4. The subject shows an elevation of AST and/or ALT ≥ 3 -fold ULN combined with an elevation of total bilirubin ≥ 2 -fold ULN (measured in the same blood sample) and/or needs to be followed up according to the 'DILI checklist' provided in the ISF.

In addition to these criteria, the investigator may remove individual subjects at any time based on his or her clinical judgment.

A subject can also be removed from the trial if eligibility criteria are being violated or if the subject fails to comply with the protocol (for instance, by non-adherence to dietary rules, or non-attendance at study assessments).

If a subject is removed from or withdraws from the trial prior to first administration of trial medication, the data of this subject will not be entered in the case report form (CRF) or trial database and will not be reported in the clinical trial report (CTR). If a subject is removed from or withdraws from the trial after first administration of trial medication, this will be documented and the reason for discontinuation must be recorded in the CRF. In this case, the data will be included in the CRF/trial database and will be reported in the CTR. At the time of discontinuation a complete end of trial examination will be performed if possible and the information will be recorded in the CRFs. If the discontinuation occurs before the end of the REP (see [Section 1.2.3](#)), the discontinued subject should if possible be questioned for AEs and concomitant therapies at or after the end of the REP in order to ascertain collection of AEs and concomitant therapies throughout the REP, if not contrary to any consent withdrawal of the subject. These discontinuations will be discussed in the CTR.

3.3.4.2 Discontinuation of the trial by the sponsor

Boehringer Ingelheim reserves the right to discontinue the trial overall or at a particular trial site at any time for any of the following reasons:

1. New toxicological findings or serious adverse events invalidate the earlier positive benefit-risk-assessment. More specifically, the trial will be terminated if more than 50% of the subjects show drug-related and clinically relevant adverse events of moderate or severe intensity, or if at least one drug-related serious adverse event.
2. The expected enrolment goals overall or at a particular trial site are not met
3. Violation of GCP, or the CTP, or the contract with BI by a trial site or investigator, disturbing the appropriate conduct of the trial
4. The sponsor decides to discontinue the further development of the investigational product.

The investigator / the trial site will be reimbursed for reasonable expenses incurred in case of trial termination (except in case of the third reason).

3.3.5 Replacement of subjects

In case a subject vomits within 8 h after trial drug administration assuming an incomplete absorption of the radiolabelled compound an additional subject may be entered and dosed to assure that 6 evaluable subjects will complete the study as per protocol.

In case some subjects do not complete the trial, the trial clinical monitor together with the trial pharmacokineticist and the trial statistician are to decide if and how many subjects will be replaced. Replacement of subjects and dosing of additional subjects as described above should always be done in mutual agreement with the principal investigator. A replacement subject will be assigned a unique study subject number, and will be assigned to the same treatment as the subject he replaces.

